2.5 Inclusion Criteria

1. 13-21 years of age
2. PHQ-8 score ≥ 5 at eligibility screening
3. English fluency and literacy (participant and legal guardian, if applicable)
4. Access to a compatible smartphone (or other device) and operating system (i.e., capable of installing the app from the Google Play or Apple App Store; list will be provided on study website [app2]) and regular internet access
5. Participant willing and able to provide informed consent/assent and have legal guardian willing and able to provide informed consent (if required)
6. Under the care of a United States (U.S.)-based licensed healthcare provider and willing and able to provide contact information for the provider and sign a HIPAA release that allows Limbix to contact provider
7. Willing and able to provide information required for study enrollment (e.g. all responses to initial PHQ-8 assessment, and current antidepressant medication status)
8. Located in the continental U.S., Hawaii, or Alaska, and not planning to leave the U.S. during the study period (through 1-month follow up assessments, up to 11 weeks after eligibility screening)

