Participants will be asked to indicate in weekly participant symptom checks (PSCs; see Appendix 1) or to notify the study team if their treatment for symptoms of depression or any other health condition changes during the study, or if they participate in any other treatment/intervention research study. Participants will be encouraged to follow the advice of their doctor regarding all medical decisions. Participants will be told that this is a blinded study, meaning that most of the study staff with whom they interact after randomization will not know whether they received the SparkRx app or not. They will be provided with contact information if they need to reach out for app or web portal troubleshooting, or with questions about their participation in the study.

After eligibility is confirmed, an account for legal guardians (if applicable) in the secure web portal will be created with usernames (user email addresses), and legal guardians will be provided a temporary password to log in to change their password. Participants and legal guardians (if applicable) will be directed to complete baseline assessments in the secure web portal. Upon completion of baseline assessments, participants will be randomized (1:1) to either the SparkRx condition or the eUC only condition (see descriptions below). Randomization will be stratified by participant-reported antidepressant medication status ([yes, no] from the Medication Use Screener) and participant-reported baseline PHQ depression severity (low: PHQ-8 score <15; high: PHQ-8 score ≥15). Participants will receive instructions on how to download and log into their assigned mobile app. Following randomization and app download, the session will end. Additional information will be sent to participants via email.

Following the videoconferencing session, research coordinators will contact participants' healthcare provider offices and indicate that the patient has enrolled in this research study. If information is volunteered to the research coordinator that the participant is not a patient of the healthcare provider, the participant will be contacted to provide information for an alternative healthcare provider. As participant safety may be compromised in the absence of a known U.S.-based healthcare provider, participants will be dropped from the

study if contact information for an alternative healthcare provider is not obtained.

Intervention Period

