- The **Patient Health Questionnaire (PHQ-8) Participant and Legal Guardian Proxy** is an 8-item participant-report measure for screening for depression and for establishing depression severity¹⁰⁰. The total score ranges from 0-24, with a higher score indicating greater depression symptom severity. For participants under 18, a legal guardian proxy version of the PHQ-8 will be administered to legal guardians. Clinically significant improvement is defined as a reduction in assessment score ≥ 5 ¹⁰¹. Intervention response is defined as 50% reduction in symptoms from pre- to post-intervention, and remission is defined as a score < 5 following intervention¹⁰².
- **Medication Use Screener** is a single-item screening form that asks participants to report whether or not (yes/no) they are currently taking psychotropic medication for the treatment of depression or symptoms of depression.
- **7 item Generalized Anxiety Disorder scale (GAD-7)**. The GAD-7 is a validated 7-item participant-reported assessment for generalized anxiety disorder¹⁰³. We will evaluate changes in anxiety symptoms given the high comorbidity between anxiety and depression. The total score ranges from 0-21, with a higher score indicating greater anxiety symptom severity.
- **Pediatric Quality of Life Enjoyment & Satisfaction Questionnaire (PQ-LES-Q) Participant & Legal Guardian**: A 15-item participant-reported self-administered questionnaire that captures life satisfaction over the past week¹⁰⁴. Each question is rated on a 5-point scale from 1 (Very Poor) to 5 (Very Good). The first 14 items are summed to form a total score ranging from 14-84, with higher scores indicating higher quality of life. The 15th item ("Overall, how has your life been?") is a stand-alone item. For participants under 18, a legal guardian proxy version of the PQ-LES-Q will also be administered to legal guardians.
- **Participant Symptom Check (Participant and Legal Guardian)**. Assesses legal guardian- and participant- reported negative symptoms and changes in treatment since the last check-in, using multiple choice and free-form text responses.

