4.5 Safety Outcomes

- Number of adverse events (AEs), number of participants with AEs, and rates of AEs based on

- PHQ-8-based symptom deterioration and responses to weekly PSC questionnaires (both groups)
- Number of AEs, number of participants with AEs, and rates of AEs based on in-app freeform text (SparkRx group only)
- Number of adverse device effects (ADEs), number of participants with ADEs, and rates of ADEs (SparkRx group only)

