4.8.1 Study Staff Responsibilities

If suicide ideation is endorsed at any point during the study, a safety protocol will be initiated. If participants are found to have a high suicide risk, they will be excluded from the research study and participants will be directed to appropriate local resources. A participant has high risk for suicide if they endorse ideation with a plan or intent. All safety incidents will be documented and reported to the DSMB, IRB, and FDA as needed.

If safety risks related to suicidality are identified during a study session, a brief suicide screening assessment (e.g., Self-Injurious Behavior Thoughts and Behavior Interview (SIBTI) may be conducted (Appendix 7). If there is an immediate concern for safety, the participant will be directed to go to the nearest ER or call 911/local behavioral health emergency responders. The study clinician will be alerted and triage safety risk as per the study safety protocol. The study clinician will contact the participant and emergency contact as needed, provide resources, and determine whether additional steps are necessary.

Symptom deterioration will be defined as a PHQ-8 score ≥ 15 and a ≥ 5 -point increase from baseline or a PHQ-8 score ≥ 20 at two consecutive timepoints. If a deterioration event occurs, an alert will be sent to the study team. Freeform text entered in the mobile app, PSC assessments, and deterioration alerts will be reviewed by study staff daily. Any correspondence from a study participant will also be reviewed. If a safety concern is identified (including endorsements of or thoughts of self-harm, harming others, or others are harming them), a study team member will notify a study clinician. The contacted study clinician will review all deterioration events and concerning freeform text and reach out to participants and emergency contacts if indicated, as per the study safety protocol. The Medical Expert clinician will determine the outcome of adverse events and unanticipated adverse device effects in consultation with the independent external clinician. Data about individual safety concerns, AEs, ADEs, and outcomes of clinical reachout may be securely shared with participants' healthcare provider or referring healthcare system upon written authorization by the participant and/or legal guardian as part of the informed consent process.

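### The second limb of the symptom-deterioration rule needs no rise from baseline, so the PHQ-8-based safety count in 4.5 mixes persistent severity with worsening

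*Combined protocol and SAP*

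**What the plan says.** Section 4.8.1 gives the only PHQ-8 definition of the term. The change limb reads: "Symptom deterioration will be defined as a PHQ-8 score ≥ 15 and a ≥ 5 -point increase from baseline". The level limb follows directly: "or a PHQ-8 score ≥ 20 at two consecutive timepoints". The stated consequence is a safety alert: "If a deterioration event occurs, an alert will be sent to the study team". A study clinician reviews each event. The Medical Expert and then an independent external clinician classify safety events as AE or ADE.

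Section 4.5 uses the same term as a safety outcome. Its lead-in is "Number of adverse events (AEs), number of participants with AEs, and rates of AEs based on", and the first source listed is "PHQ-8-based symptom deterioration and responses to weekly PSC questionnaires (both groups".

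Three other places matter. Section 3.4 on the PHQ-8: "The total score ranges from 0-24, with a higher score indicating greater depression symptom severity". Section 2.5 sets only a lower bound for entry: "PHQ-8 score ≥ 5 at eligibility screening". Section 3.1 stratifies randomization with one cut, "high: PHQ-8 score ≥15". In Table 1 the participant's PHQ-8 is taken at eligibility screening and not again in the baseline column, so the screening score appears to serve as baseline.

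**The concern.** As an alert, a rule that catches persistently severe scores is coherent. The difficulty comes when the same flag is tabulated as deterioration by arm. A participant who was severe at entry and is unchanged or slightly lower since then gets the same label as one who has risen to the top of the scale.

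The level limb depends on staying at 20 or above, which is partly an efficacy outcome. If SparkRx helps severe participants fall below 20, its deterioration count drops even if as many participants worsen as under eUC. That drop could offset a real excess of worsening in the SparkRx arm. Section 4.8 lists clinically significant worsening of depressive symptoms among both the anticipated AEs and the expected ADEs, so readers of the safety tables will look for exactly this.

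**Working it through.** **Plan's own figure.** The documents state no deterioration or AE rate, so there is nothing to reproduce. The check applies the rule to score paths and then sizes the effect under stated assumptions.

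**1. Reach of the change limb.** It needs a follow-up score of at least baseline + 5, and the maximum is 24. From a baseline of 20 that would be 20 + 5 = 25 > 24. The limb can be met only from baselines 5 to 19. For baselines 20 to 24 the level limb is the only route to a flag.

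**2. Paths (baseline → two successive scores).**
- 24 → 20 → 20: flagged, 4 points lower.
- 22 → 22 → 22 and 20 → 20 → 20: flagged, no change.
- 20 → 24 → 24: flagged, 4 points higher.

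These results are the same under four readings of the sentence: either limb alone suffices; the two-timepoint condition governs both limbs; baseline may be one of the two timepoints; or the score of 15 or more is common to both limbs. If baseline may count, 24 → 20 triggers at the first weekly score.

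**3. What a level-limb flag can mean.** Two scores from 20 to 24 give 5 × 5 = 25 possible pairs. For baseline b, pairs with neither score above b number (b − 19)², and pairs with both scores below b number (b − 20)².

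| Baseline | Neither above | Both below |
|---|---|---|
| 20 | 1 | 0 |
| 21 | 4 | 1 |
| 22 | 9 | 4 |
| 23 | 16 | 9 |
| 24 | 25 | 16 |

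These are counts of possible pairs, not probabilities. From baseline 24, no flag can reflect worsening.

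**4. Effect on an arm comparison.** Let p be the proportion who worsen and q the proportion flagged for persistence only. The difference in flags, SparkRx (1) minus eUC (0), is (p₁ + q₁) − (p₀ + q₀) = (p₁ − p₀) + (q₁ − q₀). If q₁ = q₀, the absolute difference is unchanged and only the ratio (p₁ + q)/(p₀ + q) moves towards 1. If treatment lowers persistence, q₁ < q₀ and the second term is negative whatever p does.

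**5. Size (assumed inputs; none is in the documents).** Underlying severity is normal with mean 12 or 14 and between-person SD 4.5 or 5. Independent noise of SD 2 or 2.5 is added to each score, with a linear mean improvement of 1 or 3 points over 5 weeks. Scores are rounded and held to 0–24, and participants with a screening score of 5 or more are kept. There are five weekly scores, and baseline is not an eligible timepoint. That gives 2 × 2 × 2 × 2 = 16 combinations. Participants flagged only through the level limb, with no score above baseline in any qualifying pair, were:
- 9% to 39% of all flagged participants (lowest at mean 12, SD 4.5, noise 2.5, improvement 1; highest at mean 14, SD 5, noise 2, improvement 3);
- about 3 to 12 of 220.

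A cruder bound assumes that 5% to 20% start at 20 or more and that 30% to 70% of them stay there twice without rising: 220 × 0.05 × 0.30 = 3.3 up to 220 × 0.20 × 0.70 = 30.8.

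**The case against.** The strongest reply is that the rule is an alert, placed under staff responsibilities, and that clinical review and formal classification stand between flag and count. Much of this stands. A reader might infer that the AE counts are wrong. The documents do not support that, because nowhere do they say that each flag automatically becomes one counted AE. But the steps described decide on outreach, AE versus ADE, seriousness and device relationship. None says that a flag without a rise is dropped, so the route from flag to count is left open.

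Other stronger readings also go too far:
- **That the rule labels improvers as deteriorated.** The plan's threshold for meaningful improvement is 5 points (3.4, 4.1). From 24, a score of 20 is only 4 points lower, so no one can have improved by that standard at the scores that trigger the level limb.
- **That it hides or biases a planned arm comparison.** Section 4.5 lists numbers and rates, and 4.7 plans no between-arm safety test. The rule is the same in both arms. Equal persistence leaves the absolute difference intact; the distortion arises only if persistence differs.
- **That deterioration is the only expected ADE.** Section 4.8 also names worsening mood, and ADEs are counted separately, in SparkRx only.
- **That AEs are meant purely as a measure of worsening.** The AE definition in 4.8 is broader. It does, however, concern events during the study, which fits poorly with severity already present at entry.

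It is also fair to say that weekly scores are collected in both arms, so the split could be derived later. Fixing it before data are seen by arm is still better.

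**Conclusion.** The point holds as one of labelling and reporting. The level limb counts persistent severity, unchanged or slightly reduced, as symptom deterioration, and 4.5 bases AE numbers and rates on that term. This follows from the text and the 0–24 scale and needs no assumption.

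The number affected is uncertain. About 3 to 12 of 220, or 9% to 39% of flagged participants, rests wholly on the assumed severity distribution, noise and improvement. In every combination most flags did not arise this way. How many would reach the AE tables depends on a review step that the plan does not specify. Stratifying at 15 does not directly balance the number starting at 20 or more in each arm, which is a further reason to show that subgroup separately.

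**What to change.** Change analysis and reporting only; leave the clinical alert and participant monitoring as they are. Section 4.7 says a detailed SAP is still to be written, so the following can go there.

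1. Report two counts by arm:
   - (a) worsening from baseline: the change limb, or the level limb with at least one qualifying score above baseline;
   - (b) persistent score of 20 or more with no score above baseline.

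   Label only (a) as symptom deterioration. Using the change limb alone for (a) would mean that no one starting at 20 or more could ever be counted as deteriorated.
2. Show both counts by baseline below 20 and 20 or above. Row (b) is empty below 20 by construction, because any qualifying score is then above baseline.
3. State how a flag becomes a counted AE, including whether review may remove one without a rise.
4. State whether the screening score can be one of the two consecutive timepoints.

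The cost is a few sentences and an extra table row with its baseline split. The headline deterioration count will be somewhat smaller. Under (a), a small rise such as 20 → 21 → 21 still counts and may be weekly noise; the baseline split lets a reader see how many such cases there could be.

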7.1 Risk Category

Minimal risk

7.2 Potential Risk

Psychological risks: Some personal questions about life experiences or mood may bring up uncomfortable feelings.

Loss of confidentiality: As this study involves the use of identifiable, personal information, there is a chance that a loss of confidentiality will occur though steps to mitigate this risk have been taken as described below.

7.3 Protection Against Risk

To minimize psychological risks, participants will be instructed that they can choose not to answer any question in any assessment, and can discontinue their participation at any time. Because baseline PHQ-8 score and current antidepressant medication use are required for study randomization, participants will be informed that if they choose not to respond to these questions, they will not be able to continue their participation in the study. In addition, because the SparkRx mobile app progresses in a linear fashion, questions in the mobile program must be answered to progress to the next task. During consent, participants will be informed that they may discontinue their participation at any time. Patient responses to assessments completed weekly will be monitored as well as free response answers to questions delivered via the mobile app. This will enable detection of deterioration in clinical status. If such deterioration occurs, research staff will immediately contact the PI/study clinician/Medical Expert. Participation will be terminated if clinical evidence indicates that continuing would not be in the best interest of the subject as determined by the Medical Expert in consultation with a study clinician. Participation will also be terminated if the Medical Expert determines that the subject's

safety cannot be adequately monitored and/or circumstances would prevent the safety protocol from being implemented (e.g., participant's location cannot be confirmed to be within the U.S., healthcare provider indicates that participant is not their patient and alternative provider information cannot be obtained in a timely fashion). Weekly symptom reporting will also help the research team to identify any psychological or physical health consequences of study participation and, in consultation with study clinicians and the Medical Expert, determine the best way to mitigate further risks to participant health.

No medications will be withheld; however, participants will be asked to report changes to mental health-related treatment while participating in the research study.

To minimize risks to privacy and/or confidentiality, only personnel with training in protecting private information about human subjects will have access to study data. Special care will be taken to prevent unauthorized access to data files.

Computers on which data files will be accessed will have password-protected access. All study participants will be assigned code numbers on entry to the study and all subsequent data processing will be completed by reference to these numbers. Special care will be taken to prevent unauthorized access to the database or case report forms connecting participant identity to subject numbers.

All publications or reports of data will be anonymous in relation to subject identification. Protected health information will be disclosed to other professionals treating the participant only upon written authorization of the participant (or legal guardian). PIs will retain responsibility for ensuring that files are maintained in a secure manner during and after study.

Study staff will ensure that no individuals outside the authorized team can overhear conversations during the virtual sessions. Participants in the study will be expected to complete mobile interventions at a location of their own discretion with respect to privacy and confidentiality.

Although every reasonable effort has been taken, confidentiality during Internet and phone-based communication procedures cannot be guaranteed and it is possible that additional information beyond that collected for research purposes may be captured and used by others not associated with this study.

Any data shared in the future will be stripped of all identifying information and protected health information or a limited data set may be shared with a Data Use Agreement, when applicable.

7.4 Potential Benefits to the Subjects

No direct benefits can be guaranteed by participating in this research protocol. As participants in the intervention arm will receive a mobile program designed to be therapeutic, they may experience direct benefits from participation in terms of reduced symptoms of depression, as well as potential reductions in comorbid anxiety symptoms, and improvements in mood, and/or functional outcomes.

Participants may also directly benefit from participating in the proposed research because of the knowledge obtained. Assessments and procedures completed during the study may provide participants with an opportunity to reflect on their thoughts, feelings, and behaviors which may be valuable in helping individuals better understand their own emotional functioning. These benefits outweigh the minimal risks associated with this trial. Participants will have the opportunity to provide feedback about the intervention to help improve the program for future users. This ability to help others may also have therapeutic benefits for participants.

7.5 Alternatives to Participation

Prospective participants who decline to enroll in this study are free to consider alternatives, including seeking

treatment. Standard of care treatment for adolescent depression typically includes psychotherapy with or without antidepressants, depending on clinically determined variables. Mental health resources will be shared with potential participants who decline to participate in this study but are treatment-seeking. However, alternative treatments are not promised or guaranteed. Participants may also participate in another research study or not seek any treatment.

8. Subject Identification, Recruitment and Consent/Accent

8.1 Method of Subject Identification and Recruitment

Participants will be recruited through community sampling and provider- or healthcare system-facilitated community recruitment. Contract research organizations (CROs) and other referral based recruitment companies may be used to contact potential participants, providers, and healthcare systems.

8.2 Process of Consent

Prior to participation, electronic consent will be obtained for all participants over 18. For participants under 18, electronic assent will be obtained, and electronic consent will be obtained from a legal guardian unless the minor is legally emancipated or financially independent in accordance with CA state regulations and regulations of the state in which the minor resides. Any trained member of the research team will be authorized to obtain informed consent/assent.

For consent processes that are completed virtually via videoconferencing, to ensure participant privacy, the research staff member conducting the consent process will ensure that no one outside of the research team can overhear the consent process from their end and will recommend that the potential participant join the videoconference from a private location. The researcher will provide an explanation of the study and the consent form (live or video-recorded), take time to answer any questions, provide time for decision-making, and request an electronic signature.

Participants (and legal guardians, where applicable) will be informed that their participation is voluntary, they are free to discontinue participation at any time, and all information will be kept confidential, except: 1) legally-mandated exceptions to confidentiality, e.g., if a participant reports that they are at risk of harming themselves or someone else, or that someone is harming them, and 2) legal guardians of minor participants will be informed when a study clinician determines that clinical contact with the participant or legal guardian is warranted. For example, legal guardians will be contacted if a participant under 18 years of age exhibits potential worsening of psychological symptoms as indicated in app freeform text or weekly check-in responses. Participants will be told that freeform text entries in the mobile app during the study will be reviewed, but not in real time. It will be clearly communicated to all participants that this intervention is not intended to prevent suicide attempts or self-harm behaviors and that the intervention is not for emergency care. All potential risks or discomforts will be explicitly listed and explained. Participants will also be asked to indicate whether or not they'd be willing to be contacted regarding future research opportunities. Participants will be asked if de-identified written or spoken statements they provide during the study can be used in any marketing materials or publications and can opt out from allowing any de-identified statements they provide to be shared.

Consent forms, as well as verbal presentations (videoconference and video), will additionally emphasize:

- 1) This is a research study testing an investigational medical device intended as a treatment for symptoms of depression;
- 2) Possible (minimal) risks and benefits of participation;
- 3) Participants can elect not to respond to any question(s) they are not comfortable answering, with the exception of the baseline assessments required for study enrollment;
- 4) Participants can choose to end their participation at any time for any reason;
- 5) All information will be kept confidential with the exception of certain information that must be reported for legal or ethical reasons including suspected child abuse or neglect, suspected elder abuse or neglect, or

intent to harm oneself or others.

The consent process will be considered complete only if the participant (and legal guardian, if applicable) demonstrates comprehension of all study procedures. This will be determined through comprehension questions and conversation with study staff. After all questions concerning the study have been fully answered by study staff, a Part 11 compliant, electronic signature will be obtained from the participant to document consent. Documentation of the assent of a minor will also be obtained. Participants (or legal guardians) will be required to display a valid form of identification to verify identity. Participants will be provided with a link to access and download a copy of the signed consent/assent form at any time. Signed electronic consent/assent forms will be stored in a HIPAA compliant server.

If a minor will become of legal consenting age during their participation in the study, they will be required to consent at that time to continuing their participation.

